All TMB-202 and TMB-301/311 trial participants randomized to 800 mg IBA every 2 weeks with or without a loading dose will be included in the main analyses. From the OPERA cohort, adult PWH with resistance from three ARV classes will be considered for inclusion (see section 3.2.1 for more details). OPERA PWH initiating a new non-IBA OBR between 01JAN2008 and 31DEC2020 will be included; person-time will be censored at the first of (a) initiation of a select potent ARV, (b) >45 days without ART, (c) 12 months after last clinical contact, (d) death, or (e) study end (i.e., extract date of the dataset; TBD). Viral suppression (i.e., <200 copies/mL) and undetectable viral load (i.e., <50 copies/ml) will be assessed at each of the timepoints of interest (i.e., weeks 24, 48, 60 and 96), using the closest measurement to the timepoint within a ± 6 -week window.

Statistical Analyses

Multiple imputation will be used to ensure that eligible OPERA participants can contribute to all timepoint analyses even if their routine clinical care resulted in viral loads being measured outside of the ranges defined in the protocol. To prevent the introduction of a bias towards the null, imputation will be performed in the OPERA non-IBA OBR group separately.^[18] 95% confidence intervals will be obtained through bootstrapping.

First, the data will be sampled with replacement to create 500 bootstrap samples. Within each bootstrap sample, multiple imputation will be implemented using chained equations, producing 10 imputed datasets per bootstrap sample.

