Within each imputed dataset, analyses will be performed to obtain an estimate at each timepoint for all 5,000 datasets (i.e., 500 bootstrap samples * 10 imputed datasets). Risk ratios for both viral suppression and undetectability will be estimated as a measure of comparative virologic effectiveness of IBA+OBR vs. non-IBA OBR at each timepoint. The *average treatment effect in the treated* (ATT) will be estimated using standardized mortality ratio (SMR)-weighting, a form of propensity score (PS)-weighting. SMR-weighting ensures that the distribution of baseline characteristics is the same in the control population as in the treated population.^[20] In other words, the external control population will be weighted to look like the treated population. Logistic regression will be used to obtain the PS and will include baseline values for important predictors of regimen selection. SMR weights are set to 1 in the treated population (i.e., TMB trials IBA+OBR) and to PS/(1-PS) in the control population (i.e., OPERA non-IBA OBR).^[20] The final set of variables included in the PS model will be determined by the distribution of weights, as well as the balance of covariates across groups before and after applying SMR weights.

Estimates of risk will be derived from SMR-weighted Kaplan-Meier curves. The cumulative probability of viral suppression or undetectability will be estimated at each timepoint of interest for each arm, from which risk ratios will be calculated. Estimates will be averaged across all datasets to obtain the combined estimate and 95% confidence intervals will be derived from the distribution of all estimates, using the 2.5th & 97.5th percentiles.

These analyses will be repeated for sensitivity objective 1 after restricting the OPERA non-IBA OBR group to PWH with a VL >1,000 copies/mL. For sensitivity objective 2, analyses performed using the European registry data will be replicated as closely as possible, taking into consideration the differences in design between the registry and OPERA datasets.

1. Background and Rationale

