3.2.2. Study Timelines

Study timelines are mapped out for the two trials and for OPERA in [Table 1](#).

TMB-202

- Recruitment: 2008-2010
- Follow-up: through week 24
- Index: date of first IBA infusion

TMB-301/311

- Recruitment: 2015-2018
- Follow-up: through week 96
- Index: date of first IBA infusion

⁴ CAB had not yet been approved at the time and is not indicating for ART-experienced PWH who are failing their current regimen

OPERA

- Identification of study participants: 01JAN2008 to 31DEC2020
- Censoring criteria:
 - Initiation of any of the following ARVs:
 - INSTI
 - PI
 - Fusion inhibitor (FI)
 - Gp120 inhibitor
 - IBA
 - Doravirine
 - Blinded ARV
 - >45 days without ART
 - 12 months after last clinical contact (i.e., telephone contact, visit, lab test, or consultation)
 - Death
 - Study end (i.e., extract date; TBD)
- Index: date of regimen initiation

Table 1. Alignment of study timelines for the clinical trials and OPERA

	Week -1	Index	Week 1	Week 24	Week 48	Week 60	Week 96
TMB-202	Failing Regimen	IBA 2000mg every 4 weeks + OBR ^a					
		IBA 800mg every 2 weeks + OBR ^a					
TMB-301/311	Failing Regimen	IBA 2000mg + Failing Regimen		IBA 800mg every 2 weeks + OBR ^a			
OPERA	Failing Regimen	Index regimen ^b					

^a Changes in OBR were allowed during follow-up

^b Some changes in ARVs will be allowed to be consistent with trial designs; person-time will be censored at initiation of an INSTI, PI, fusion inhibitor, Gp120 inhibitor, IBA, doravirine or a blinded ARV

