TDF, TAF	NA	Includes one of: K65R, K65N Without M184V, M184I	Includes one of: K65R, K65N With M184V or M184I	NA	M184V/I confers resistance to other drugs but increases sensitivity to TDF, TAF
FTC, 3TC	NA	Includes one of: M184V, M184I	Includes one of: K65R, K65N	NA	NA
ETR	NA	Includes one of: K101P, Y181I, Y181V OR Two of: L100I, K101EH, Y181C, G1190E, G190Q, H221Y	Includes one of: L100I, K101EH, Y181C, G190E, G190Q, H221Y	NA	NA

Covariates for the multiple imputation model

The following characteristics are available in OPERA but may or may not be available in the TMB-202 and TMB 301/311 datasets. These baseline and time-updated characteristics may be used for the multiple imputation model, as predictors of the value of viral loads at timepoints of interest.

- Age at regimen initiation
- Sex at regimen initiation
- Race
- HBV co-infection at regimen initiation
- HCV co-infection at regimen initiation
- AIDS (ever)
- Viral load at each timepoint
- Viral loads in between timepoints
- Timing of viral loads
- CD4 cell count at each timepoint
- CD4 cell count in between timepoints
- Timing of CD4 cell counts
- Index date
- ARVs in index regimen
- Resistance to ARVs
- Number of anchor agent classes exposure prior to index

4. Data Analyses

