4.1. Bootstrapping

Bootstrapping will be employed to obtain confidence intervals around the study estimates. First, the data will be sampled with replacement to create 500 bootstrap samples. Within each bootstrap sample, multiple imputation will be implemented, producing 10 imputed datasets per bootstrap sample. Within each imputed dataset, analyses will be performed to obtain an estimate at each timepoint for all 5,000 datasets (i.e., 500 bootstrap samples * 10 imputed datasets). The combined estimate will correspond to the average of all 5,000

estimates and the 95% confidence interval will be derived from their distribution, using the 2.5th & 97.5th percentiles.

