4.2. Multiple Imputation

OPERA data represent routine clinical care in the US. Therefore, the timing and frequency of follow-up visits and testing varies across patients and providers. Such variations may give rise to a missing data problem in analyses relying on outcomes measured at specific timepoints. While windows have been established around each timepoint of interest to increase the number of VL measurements available for analysis, it remains likely that VL will be missing for different PWH in different time windows.

Complete case analysis in which observations with missing data are omitted is appropriate when data are *missing completely at random* (MCAR; i.e., the missing values do not depend on observed or unobserved data).^[33, 34] With any other type of missing data, despite being the simplest and most commonly used strategy, complete case analysis can lead to severe bias.^[33, 34] In addition, complete case analysis reduces the analytical sample size, thus reducing the efficiency of estimations.^[33]

Limitations of complete case analyses may be alleviated with imputation of missing values when data are *missing at random* (MAR; i.e., the missing values depend on observed data only).^[35] Multiple imputation means that multiple values are imputed for each missing value, resulting in multiple complete datasets. Statistical analyses are then conducted on each imputed dataset, and the results are combined.^[35] Multiple imputation relies on predictive models to predict the missing values based on the observed data. It is therefore important to include all variables that could help predict the missing values.^[18]

Within each bootstrap sample, multiple imputation will be used to ensure that eligible OPERA participants can contribute to all timepoint analyses even if their routine clinical care resulted in VL being measured outside of the ranges defined in the protocol. Missing VLs in OPERA will be handled with multiple imputation implemented using chained equations to produce 10 imputed datasets.

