4.4. Primary Objective: External Comparison of Virologic Effectiveness

The comparative virologic effectiveness of IBA+OBR vs. non-IBA OBR will be assessed at each timepoint for both viral suppression (VL < 200 copies/ml) and undetectability (VL < 50

copies/ml). Within each imputed dataset, estimates of risk will be derived from SMR-weighted Kaplan-Meier curves. The cumulative probability of viral suppression or undetectability will be estimated at each timepoint of interest for each arm, from which risk ratios will be calculated.

The distribution of estimates from all 5,000 datasets will be used to obtain the final estimate (mean) and 95% confidence intervals (2.5th and 97.5th percentiles).

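### The 95% limits are percentiles of 5,000 single-imputation risk ratios while the reported risk ratio averages over imputations, so the interval is too wide for that estimate; the mean of bootstrap ratios also tends to sit slightly high

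*Combined protocol and SAP*

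**What the plan says.** The rule appears three times and is consistent. Section 4.1 (Bootstrapping) draws 500 bootstrap samples, imputes each 10 times, takes the average of the resulting 5,000 RRs as the combined estimate, and adds that "the 95% confidence interval will be derived from their distribution, using the 2.5th & 97.5th percentiles". The synopsis (Statistical Analyses) has "95% confidence intervals will be derived from the distribution of all estimates", and section 4.4 repeats it for the primary objective: "The distribution of estimates from all 5,000 datasets will be used to obtain the final estimate (mean) and 95% confidence intervals". Section 4.5.1 carries sections 4.1-4.4 into sensitivity objective 1.

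Nowhere are the 10 imputations averaged within a bootstrap sample before percentiles are taken, and no between/within variance correction is given. No estimate from the original, unresampled data is planned as the point estimate.

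Only the control arm is imputed: "imputation will be performed in the OPERA non-IBA OBR group separately" (synopsis). Section 4.2 expects missing values, since "it remains likely that VL will be missing for different PWH in different time windows", but gives no rate.

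**The concern.** The interval and the estimate describe different quantities. Each of the 5,000 RRs carries the noise of its own imputation draw. The reported RR has averaged that noise away, but the percentiles keep all of it, so the stated uncertainty belongs to a single-imputation estimate that nobody reports.

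The loss is of precision, in a study with 99 treated participants and about 200 controls. It also works against the plan's own reasons for its methods: section 4.2 favours imputation partly because complete-case analysis is less efficient, and section 4.3 chooses weighting partly for power.

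A second, separate issue is the point estimate. The arithmetic mean of bootstrap ratios is not the ratio found in the actual data, and averaging ratios on the natural scale tends to push the result upward, here towards IBA. Pooling the imputations does not cause this shift, and the shift does not move the percentile limits.

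**Working it through.** **The plan's own figure.** 500 x 10 = 5,000, as stated. The documents give no interval width, missing fraction or suppression rate, so nothing else can be reproduced.

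**Inputs from the documents.** Treated: 59 + 40 = 99 (section 5). For TMB-202, "Follow-up: through week 24" (section 3.2.2); 27 of the 40 TMB-301 patients entered TMB-311 (section 3.1.2), so 27 are followed beyond week 24. Controls: about 200 (section 5).

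**Assumptions.** Missing control viral loads f = 20%, 40% or 60%; control suppression risk p0 = 0.40 and treated p1 = 0.52 (RR 1.3); effective control size after weighting 125; share of outcome variance explained by the imputation predictors R2 = 0 (uninformative) or 0.48 (predictor agreeing with the missing value 85% of the time).

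**Closed form on log RR.**

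- V1 = (1 - p1)/(n1 x p1) = 0.48/(99 x 0.52) = 0.0093
- V0 = (1 - p0)/(ESS x p0) = 0.60/(125 x 0.40) = 0.0120
- Complete-data variance W = V1 + V0 = 0.0213
- Between-imputation variance B = V0 x (1 - R2) x f/(1 - f)

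An RR from one imputation of one bootstrap sample has variance W + B from sampling plus B from the imputation draw: W + 2B. Averaging 10 imputations first leaves W + B + B/10 = W + 1.1B. The width ratio is sqrt((W + 2B)/(W + 1.1B)).

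- f = 0.4, R2 = 0: B = 0.0080; sqrt(0.03732/0.03012) = 1.113
- f = 0.4, R2 = 0.48: B = 0.0042; sqrt(0.02964/0.02590) = 1.070
- The same formula gives 1.053 and 1.030 at f = 0.2, and 1.181 and 1.125 at f = 0.6.

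**Simulation of the planned estimator type.** Under section 4.4, "estimates of risk will be derived from SMR-weighted Kaplan-Meier curves". I simulated weighted Kaplan-Meier curves to first suppression, with 59 + 13 = 72 treated censored after week 24 and 27 continuing, 200 controls (effective size about 122), and chained logistic imputation. There were 50 datasets per cell and 150 bootstraps x 10 imputations. The table shows the SD of single-imputation log RRs divided by the SD of 10-imputation averages (Monte Carlo SE 0.001-0.007).

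| Missing | Predictor | Wk 24 | Wk 48 | Wk 60 | Wk 96 |
|---|---|---|---|---|---|
| 20% | uninformative | 1.048 | 1.030 | 1.029 | 1.029 |
| 20% | 85% agreement | 1.029 | 1.018 | 1.017 | 1.018 |
| 20% | 95% agreement | 1.019 | 1.012 | 1.010 | 1.011 |
| 40% | uninformative | 1.110 | 1.086 | 1.078 | 1.072 |
| 40% | 85% agreement | 1.078 | 1.054 | 1.045 | 1.040 |
| 60% | uninformative | 1.196 | 1.158 | 1.144 | 1.129 |
| 60% | 85% agreement | 1.159 | 1.119 | 1.106 | 1.094 |

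**Against complete-case analysis.** With data missing completely at random, the complete-case variance is V1 + V0/(1 - f) = W + V0 x f/(1 - f). The planned W + 2B is smaller only if 2(1 - R2) < 1, that is R2 > 0.5. At f = 0.4 and R2 = 0.48 the planned width is sqrt(0.02964/0.02932) = 1.01 times the complete-case width; averaging first gives sqrt(0.02590/0.02932) = 0.94. With such a predictor the planned rule gives up the efficiency gain from imputing.

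**Point estimate.** If bootstrap RRs are roughly lognormal, their mean exceeds their median by a factor of about exp(variance/2). With the variance of 0.0296 above, exp(0.0148) = 1.015. In the Kaplan-Meier runs the mean bootstrap RR was 1.016-1.049 times the original-data RR at week 24 and 0.997-1.011 times later. In a single-visit simulation (99 treated, 200 controls, 380 datasets per setting) it was 1.016 and 1.029 times at 30% and 60% missing, above the original-data RR in 98-99% of runs, while the geometric mean showed no shift. With only 100 controls and control risk 0.30 the ratio was 1.066 and 1.094 at 20% and 40% missing, and unstable at 60%.

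**The case against.** The strongest reply concerns coverage. In a single-visit simulation of 12 cells (99 or 27 treated, RR 1.0 or 1.3, 450 datasets each, 500 x 10), mean coverage was 0.956 as planned, 0.964 for a normal interval built on the 500 averages, and 0.944 for percentiles of the 500 averages. The planned rule is thus no further from 95% than either alternative. With 27 treated and RR 1, two-sided error at 20/40/60% missing was 7.1/5.6/3.1% as planned and 2.9/3.1/2.0% for the normal interval, so the replacement was more conservative there. The power gain is small: at RR 1.3 with 99 treated, the lower limit exceeded 1 in 41/35/27% of runs as planned and 39/35/29% with the normal interval.

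The top of the range also needs 60% missing and an uninformative model, whereas section 3.3.3 lists useful predictors, among them "Viral loads in between timepoints". Coverage was checked only for weighted proportions at one visit, not for the Kaplan-Meier estimator.

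Much of this stands. The excess width should not be read as guaranteed over-coverage: with few treated and little missing data, percentile limits can fall below 95% for other reasons. Planned coverage ranged from 0.929 to 0.980 in these cells and was 0.982-0.987 in the 380-dataset runs. Greater power is not the reason to change.

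It does not rescue the rule. Coverage near nominal in some settings comes from errors that partly offset, and the balance moves with missingness. In six further single-visit cells the normal interval was narrower than the planned one in every cell, with coverage of 0.953-0.970.

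**Conclusion.** The concern holds. The rule is explicit, and its limits are wider than the reported estimate warrants whenever control viral loads are imputed. The direction is certain; the size is conditional. For 20-60% missing it is about 1-20% on the log scale: at most 5% at 20% missing, 4-11% at 40%, and 9-20% at 60%. The point-estimate shift is separate, usually small, and mostly towards IBA.

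The percentages assume data missing completely at random, one propensity covariate, no regimen-change censoring of controls, and the stated risks and effective control size. The flaw does not threaten the study's conclusions by itself, but it affects both outcomes at all four timepoints and sensitivity objective 1. It should be corrected before results are seen, because narrowing intervals afterwards would look selective.

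**What to change.** Amend sections 4.1 and 4.4 and the synopsis as follows.

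- **Point estimate:** multiply impute the original data, average log RR over the imputations, and exponentiate.
- **Interval:** within each of the 500 bootstrap samples, average log RR over its 10 imputations. Report the original-data log RR +/- 1.96 x the SD of the 500 averages, back-transformed.
- **Secondary interval, if wanted:** the 2.5th and 97.5th percentiles of the 500 averages, with a note that these can slightly under-cover (0.93-0.96 in the 12 cells).
- **Near-zero control risks:** state in advance how a resample with a weighted control risk at or near zero is handled, because the SD of log RR is sensitive to it.
- **Scope:** apply the same rule to sensitivity objective 1. The complete-case replication in section 4.5.2 involves no imputation and is unaffected.

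The cost is one imputation run on the original data, a small code change and SAP wording; the 5,000 fits are reused. The interval becomes narrower, most clearly where much is missing. In the 12 cells the change in power with the recommended interval ran from -2 to +5 percentage points.

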4.5. Sensitivity Analyses

4.5.1. Impact of the viremia threshold in the OPERA non-IBA OBR group

In the TMB-202 and TMB-301/311 trials, the protocol restricted trial participation to individuals with a VL >1,000 copies/mL at baseline. However, in practice, individuals with a baseline VL ≤1,000 copies/mL were recruited. In routine clinical care, changes in regimen often occur before a threshold of VL >1,000 is reached. Therefore, to maximize the sample size and align with the population recruited in the trials, the main analysis will include PWH with a viral load > 200 copies/mL at the start of the index regimen in the OPERA non-IBA OBR group. However, to assess the impact of this more lenient threshold, a sensitivity analysis will be conducted in which the OPERA non-IBA OBR group will be restricted to PWH with a VL >1,000 copies/mL at index, as was intended for the trials.

Analyses described in sections 4.1-4.4 will be repeated after restricting the OPERA non-IBA OBR group to those with an index VL >1,000 copies/mL. New bootstrap samples and imputed datasets will be generated, within which SMR-weighted risk ratios will be estimated before being combined in a final estimate.

6.1. Limitations of Proposed Methods

With approximately 14% of the HIV population that is linked to care in the OPERA database (per the CDC estimates), OPERA can provide detailed information on a large portion of the HIV population in the US. Even so, issues confronting population-level assessments include such aspects as differential medical care by practice size and specialty, academic and research orientation of the health care practitioner, ethnic-based and

gender-based attitudes and geographic regional health care practices. OPERA clinical data is collected at point-of-care and is subject to the record-keeping practices of each healthcare provider and the standards of each clinic or organization. Patients may see multiple physician practices for various conditions, which may result in incomplete case ascertainment. Data is collected for the medical management of patients and is not directly intended for research purposes, but rather for the care and management of individual patients and patient populations.

This study is an indirect comparison of data from two clinical trials and from the OPERA observational cohort. While most trial participants were in the US, differences in the distribution of key characteristics may still impact comparability of the groups. Moreover, in the main analysis, the sample size for the IBA+OBR group is limited to 99 participants on two different dosing schedules. Sensitivity analyses have been planned to assess the robustness of findings to different design choices.

6.2. Quality Control & Quality Assurance

Epividian has working practices and procedures governing the use of observational data, development of analysis specifications and plans, the development of analytical programming and the analytical quality assurance (QA) process and the scientific review of reports as well as clinical advisory charters for the clinical review of output intended for public domain. Working practices for the development of analysis specifications include basic identifying information, background material, relevant definitions of key study variables, population definitions, baseline definitions, specific requirements for dataset creation, and statistical requirements such as eligibility criteria, exposures, outcomes and model fitting. Working practices for programming include naming conventions, proper code documentation and commentary, content, appearance, efficiencies (i.e., use of macros), and organization of output, maintainability and generalizability. Working practices for programming QA include self-reviews of observational counts, missing data values, many-to-many merges, variable formatting, numeric-character & character-numeric conversions, uninitialized variables, unresolved macro references, report completeness and report-to-specification correspondence, and system errors and logs. The QA team review may include small sample spot-checking, coding log reviews, complete coding review, selected observations from intermediary dataset reviews, and/or independent programming to reproduce the results. Documentation of non-public domain reports includes market, scientific, statistical, and clinical review. Documentation of scientific protocols, reports and manuscripts intended for public domain follows two sequential steps: an internal-to-Epividian epidemiological, statistical, and clinical review, followed by a clinical/epidemiological external advisory board review.

All analytical data, coding algorithms, QA documentation and report outputs will be retained per Epividian standard practices.

